- ii) Participants will start with 1st and 2nd Line therapy as recommended by the AUA guidelines (AUA guidelines categorize treatments as 1st through 6th Lines of care) and we will record the numbers of participants that accelerate to higher lines of therapy. *Hypothesis: IC/BPS participants treated with mindfulness & yoga + Standard of care will have fewer participants who accelerate to higher Lines of care compared to those treated with Standard of care alone.*
- iii) Participants will record pain, function and other IC/BPS symptoms using validated questionnaires at baseline and at follow-up (approximately at 6 and 12 weeks of treatment). *Hypothesis: IC/BPS participants treated with mindfulness & yoga + Standard of care will have greater improvement in pain, function and other IC/BPS symptoms compared to participants treated with Standard of care alone, based on validated questionnaires.*
- iv) Cost-analysis will be performed comparing treatment groups. *Hypothesis: Cost analysis will find that those treated with mindfulness & yoga + Standard of care will incur less cost than Standard of care alone.*
- v) Qualitative outcomes will be obtained with an optional response during the weekly interviews to see how participant's feel their treatment is going. At a later time we may go back and enter quotes into qualitative software for analysis of themes. *Hypothesis: Patients in the mindfulness & yoga + Standard of care may feel more empowered about their health.*

2. Background

IC/PBS is a chronic urologic pain disorder associated with significant morbidity. It is defined by the American Urogynecological Association (AUA) as “a complex sensation (pain, pressure, or discomfort) perceived to be related to the urinary bladder, associated with lower urinary tract symptoms of more than 6 weeks duration, in the absence of infection or any other identifiable causeⁱ.” A 2015 survey of 1,982 patients with IC/BPS noted that, of the 180 treatment modalities, none were truly effective. In the survey, patients were surveyed about their usage of complementary and alternative medicine (CAM). Of those who responded, 84.2% had tried CAM and 55% had been recommended CAM by their physiciansⁱⁱ. There are many reasons as to why patients turn to CAM, including side effects experienced from traditional therapies, lack of efficacy and frustration with providersⁱⁱⁱ.

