5.3 Sample size calculation: The primary outcome for this study is a linear mixed model of GRA variation over time. Weekly GRA and O'Leary-Sant values will be obtained on all participants. We will then further characterize patients as either treatment responder or non-responders, with treatment response defined as "moderate (+2)" or "marked (+3)" improvement on the GRA. We used previously reported outcomes from an RCT regarding impact of medication on ICBPS symptoms.

Given that we will be performing a linear mixed model, we powered our study to detect a 30% change in treatment response between groups on the GRA, with baseline response rate of 26%. We require 41 participants/group (total N=82) to obtain 80% power ($\alpha=0.05$), assuming an effect size of 0.85. Allowing for a dropout rate of 15%, we aim to randomize 94 women (47/group). We will be able to recruit the required number of participants. We see 12-15 new patients with ICBPS per month and should

be able to adequately recruit 6-7 patients/month, allowing us to meet the necessary sample of patients within 14 months of study initiation. Despite COVID-19, we still continue to care for this number of patients. The study has maximized digital & phone contact and minimized in-person contact. We foresee that we should meet our recruitment aims despite the pandemic's restrictions.

6. Study Timelines

6.1 Based on current clinic volume in the UNM division of the Urogynecology, from which we are recruiting, we estimate that recruitment of 60-120 patients will be feasible over approximately 2-3 years. Per chart review, the urogynecology division sees patients who meet criteria for this study at the rate of 10-20 per month. Assuming that approximately 25% of patients will agree to study participation (due to issues of time commitment and eligibility criteria), we believe that we will be able to recruit an appropriate number of patients in approximately 2-3 years. We believe that an additional 3 months will be needed for follow up data. We anticipate that data analysis and manuscript writing will take an additional 6-9 months.

7. Study Endpoints

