THERAPY ESCALATION: We will record when and what women use that is greater than 1st line and 2nd line therapies during their participation in the study. They will discuss escalation of therapy with their provider and study personnel will record the additional therapy as an outcome measure. This will be utilized to perform cost utility analysis to determine if the intervention is cost-effective.

PSEQ-2: The Patient Self-Efficacy Questionnaire Short Form is a 2 question questionnaire that has been used in multiple chronic pain conditions to

PROTOCOL TITLE: MYPAICE: Mindfulness and Yoga for Pain with Interstitial Cystitis Evaluation

document feelings of self-efficacy. The Short form is validated in chronic pelvic pain^{xiv}. This will be collected at baseline and at 12 weeks.

PROMIS-PI: The PROMIS-Pain interference short form 6B is an NIH PROMIS measure that measures the extent that pain interferes with daily activities. It is comprised of 6 questions^{xv}. This measure will be collected weekly.

HADS: This is formally called Hospital Anxiety/Depression Scale. This is a 7 item inventory that assesses generalized anxiety including: tension, worry, fear, difficulty relaxing and restlessness^{xvi}. This measure will be collected at baseline and at 12 weeks.

Euroqol-5d. (EQ-5d) This is a validated measure utilized to measure health states^{xvii}.

O'Leary-Sant Interstitial Cystitis Symptom and Problem Index:

This validated survey assesses severity of symptoms and bother in IC/BPS and is commonly used for IC/BPS trials. Symptom index, which has been explicitly analyzed in a prospective trial to detect change, and problem index are to be separately analyzed^{xviii}

Data Analysis

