Data Analysis: Between and within group differences will be evaluated using chi-square analysis as deemed appropriate by the statistician involved in study analysis (e.g. Fisher's Exact test for non-normal distributions of categorical variables and T-test for continuous variables). Differences between groups will be evaluated using Chi-square analyses for categorical variables as deemed appropriate by the statistician involved in study analysis (e.g. Fisher's Exact test for non-normal distributions). T-tests will be utilized for continuous variables, with comparison by Mann Whitney U for non-normal distributions. Within-group differences over time will be analyzed using the McNemar's test. If any baseline differences exist between the groups, a regression or multivariable analysis will determine the contribution of these differences to observed differences between groups. As the GRA and O'Leary-Sant will be collected more frequently, we plan to analyze these results with linear mixed models analysis.

Power Analysis: Power analysis was performed based on previously reported means and standard deviation from treatment effect based on GRA. We assumed that 41 patients in each arm (total 82) would be required to find a difference of 30% between group's pain scores (the primary outcome) with 80% power and alpha of 0.05. In order to achieve power we will need a total of 82 patients. Assuming an approximate 20-25% dropout or loss to follow-up rate, we will plan to randomize approximately 60-120 patients.

13. Provisions to Monitor the Data to Ensure the Safety of Subjects

A DSMB will not be monitoring safety of these procedures as the study risks are low. The intervention arm includes mindfulness and yoga, both of which have been shown to be low-risk interventions with minimal adverse events^{xix}. The control group will undergo standard of care treatments. Theoretically, there could be increased muscle soreness noted in patients in yoga treatment arm. There are no documented adverse events with mindfulness practice.

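### PROMIS-PI is collected weekly but left out of the linear mixed model, although the plan's reason for using that model applies equally to it

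*Combined protocol and SAP*

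**What the plan says.** - **Baseline.** Section 12 (Study Procedures) includes PROMIS-PI in the surveys completed after enrolment, and randomisation waits until all baseline data are in.
- **Follow-up.** Under Outcome measures in section 12, PROMIS-PI is the instrument that "measures the extent that pain interferes with daily activities", and the entry ends "This measure will be collected weekly". Section 5.3 has the same frequency for two other instruments: "Weekly GRA and O'Leary-Sant values will be obtained on all participants". For PSEQ-2 the entry reads "This will be collected at baseline and at 12 weeks", and for HADS "This measure will be collected at baseline and at 12 weeks".
- **Objective.** Section 1.3 (iii) has pain, function and other symptoms recorded "at baseline and at follow-up (approximately at 6 and 12 weeks of treatment"), with greater improvement as the hypothesis.
- **Endpoint.** Section 7.1 lists PROMIS-PI among several unranked secondary questionnaires, with no time point and no choice between value and change.
- **Analysis.** The Data Analysis text says that the GRA and O'Leary-Sant "will be collected more frequently, we plan to analyze these results with linear mixed models analysis". Other continuous variables go to t-tests, or to Mann-Whitney U if not normal. A regression or multivariable analysis follows if the groups differ at baseline.
- **Withdrawals.** Section 14 (Withdrawal of Subjects) intends to use a woman's data up to the point of withdrawal.

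**The concern.** The plan gives a reason for its mixed models, namely frequent collection, and then does not apply it to the third instrument that is collected weekly. As written, PROMIS-PI has no longitudinal analysis, no time point, and no baseline adjustment that is fixed in advance.

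Three things are at stake. Weekly scores that participants have already supplied may be ignored. Women who leave before week 12 would be missing from a week-12 comparison, which fits poorly with the intention in section 14. And in an unmasked trial, the choice among the last value, the change and some weekly summary would stay open until the data are seen. The outcome is secondary and the primary GRA analysis is not affected. Still, pain and function are part of the objective in section 1.1.

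**Working it through.** **The plan's own figure.** Section 5.3 needs 41 per group for a 26% response rate against 56% (reading the 30% as percentage points), with 80% power and alpha 0.05, taken as two-sided. With pooled proportion 0.41:

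n = [1.96 × √(2 × 0.41 × 0.59) + 0.84 × √(0.26 × 0.74 + 0.56 × 0.44)]² / 0.30² ≈ 41.

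This reproduces, but it concerns the GRA. The documents give no standard deviation, correlation or target difference for PROMIS-PI, so what follows is illustrative.

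**Which rule applies to each instrument**

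| Instrument | Stated follow-up | Named in the mixed model |
|---|---|---|
| GRA | weekly | yes |
| O'Leary-Sant | weekly | yes |
| PROMIS-PI | weekly | no |
| PSEQ-2, HADS | week 12 | no |

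PROMIS-PI is the only instrument stated to be weekly that is left to the general rule.

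**Value of baseline adjustment.** Assume equal variances at baseline and week 12, with correlation r between them. Relative to a raw week-12 comparison (variance 1), a comparison of change has variance 2(1 − r) and a baseline-adjusted comparison has 1 − r². The gain is the ratio of variances, read as a multiple of the sample. Against change, the variance ratio is (1 − r²) / [2(1 − r)] = (1 + r)/2.

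| r (assumed) | Change, 2(1 − r) | Adjusted, 1 − r² | Gain over raw week 12 | Gain over change |
|---|---|---|---|---|
| 0.3 | 1.40 | 0.91 | 1/0.91 = 1.10 | 1.40/0.91 = 1.54 |
| 0.5 | 1.00 | 0.75 | 1/0.75 = 1.33 | 1.00/0.75 = 1.33 |
| 0.7 | 0.60 | 0.51 | 1/0.51 = 1.96 | 0.60/0.51 = 1.18 |

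**The same in power**, for an assumed 0.5 SD difference at 41 per group (normal approximation, two-sided 0.05): Φ(0.5 × √(41/2) / √v − 1.96), where v is the relative variance.

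- Raw week-12 t-test: 62% at any r.
- t-test on change: 48%, 62% and 83% at r = 0.3, 0.5 and 0.7.
- Baseline-adjusted week 12: 66%, 74% and 89%.

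**Dropout.** Section 5.3 pairs 47 per arm with 15% dropout: 47 × 0.15 ≈ 7 women per arm. This is the most who could add earlier weekly scores. It assumes that each gave at least one, and the plan says nothing about when dropout occurs.

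**The case against.** **No sentence assigns PROMIS-PI an unadjusted t-test.** A reader might infer one, but that goes beyond the text. The general rule also allows Mann-Whitney U and a regression when baseline differences appear. The word improvement in the hypothesis of 1.3 (iii) suggests change from baseline, and a change score does use the baseline. This objection stands. What remains is that the analysis is unspecified and that adjustment depends on the observed data.

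**The efficiency figure depends on the comparator.** The upper end, about 2.0 times the sample, needs both r = 0.7 and a raw week-12 t-test. Against change at the same r it is about 1.2. It also measures baseline adjustment, not the use of weekly values. The plan does not specify a baseline covariate for O'Leary-Sant either, so adding PROMIS-PI to that model unchanged would not bring this gain. This too stands.

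**The schedule mismatch is small.** Weekly collection includes weeks 6 and 12, and 1.3 (iii) is a summary line. A reader might go further and see a conflict with the PSEQ-2 and HADS schedules. But 1.3 (iii) speaks of pain, function and IC/BPS symptoms, and those two measure self-efficacy and anxiety or depression. No conflict is shown.

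**Dropout cannot be read as larger than this.** The 20-25% rate in the Power Analysis text is paired there with 60-120 randomised. Applying it to 47 per arm would mix two plans.

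**Conclusion.** The point holds as an improvement to a secondary analysis. PROMIS-PI is measured at baseline and weekly, the stated reason for a mixed model covers it, and it is not named. For r of 0.5 to 0.7, a pre-specified baseline covariate is worth about 1.3 to 2.0 times the sample against a raw week-12 t-test and about 1.2 to 1.3 times against a t-test on change. No value in the documents supports a particular r.

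Up to about 7 women per arm could contribute partial data. Each would count for less than a completer, and the estimate would rest on dropout being explained by the scores already observed.

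A reader might infer a much larger gain from averaging 12 weekly scores: power of about 99% in the same illustration. That assumes a constant effect from week 1 and answers a different question from the week-12 difference, so it is not claimed here.

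**What to change.** - Name PROMIS-PI in the Data Analysis text. Fit a linear mixed model to the weekly scores with arm, week and arm-by-week terms and the baseline score as a pre-specified covariate, and report the week-12 arm difference with its confidence interval.
- State that scores up to withdrawal enter the model, which gives effect to section 14 for this outcome.
- As a minor wording point, align 1.3 (iii) with the weekly schedule for PROMIS-PI and O'Leary-Sant. A single schedule table would do this. It could also record follow-up times for the visual analog scale and the EQ-5D, for which none are given.

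The cost is a few sentences and a little analysis work, with no new data and no change in sample size. It should be settled before outcome data are examined by arm.

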43. Other Waiver Types (Checklist)	29
44. Vulnerable Populations (Checklist)	29

PROTOCOL TITLE: MYPAICE: Mindfulness and Yoga for Pain with Interstitial
Cystitis Evaluation

45.	Medical Devices (Checklist).....	35
46.	Export Control (Checklist)	36
47.	Data Transfer/Sharing (Checklist).....	36
48.	Specimen Transfer/Sharing (Checklist).....	37

1. Objectives

1.1 The objective of this research is to perform a non-masked, randomized clinical trial to assess pain levels and function and level of care required by patients with interstitial cystitis/painful bladder syndrome (IC/BPS) randomized to treatment with mindfulness and yoga + standard of care compared to standard care alone. Standard of care for IC/BPS is defined as treatments recommended in the American Association of Urology (AUA) guidelines (see Table 1). The target population is patients who have IC/BPS and are willing to be randomized to mindfulness/yoga therapy or standard of care therapies

Table 1: AUA Treatment Guidelines for IC/PBS

First Line	General relaxation/ Stress management, pain management, patient education, self-care, behavioral modification
Second Line	Appropriate manual physical therapy techniques, oral agents including: amitriptyline, cimetidine, hydroxyzine, PPS, intravesical instillation of DMSO, heparin, lidocaine.
Third Line	Cystoscopy under anesthesia with hydrodistension, treatment of Hunner's lesions if found.
Fourth Line	Intradetrusor Botulinum Toxin A, Neuromodulation.
Fifth Line	Cyclosporine A
Sixth Line	Diversion with or without cystectomy, substitution cystoplasty

1.2 Our central hypothesis is that IC/BPS participants treated with yoga and mindfulness will have greater improvement in their symptoms than those treated with standard of care alone. Specifically:

1.3 Outcomes & Hypotheses:

- i) IC/BPS participants treated with mindfulness and yoga will assess their response to treatment based on the Graded Response Assessment (GRA) scale (described below) at 3 months compared to standard care participants.
Hypothesis: IC/BPS participants treated with mindfulness & yoga + Standard of care will have superior scores on the GRA scale compared to those treated with Standard of Care alone.

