We will perform an unmasked, randomized controlled trial comparing yoga and mindfulness impact on 1) treatment response 2) level of treatment required 3) pain, activity and quality of life for patients with IC/BPS compared to standard care alone as recommended by the AUA (Table 1). The target population will be those patients with IC/BPS who are cared for by the urogynecology, gynecology and urology specialties. After obtaining informed consent, women will be randomized to either yoga & meditation + Standard of care compared to Standard of care alone. Masking is not possible with this study design, as participants randomized to the yoga/mindfulness versus standard of care will clearly know their treatment arm.

4. Inclusion and Exclusion Criteria

4.1 We will recruit patients who present with IC/BPS per the AUA definition. To confirm the diagnosis of IC/PBS, We will also administer the O'Leary-Sant Interstitial cystitis Symptom Index and Problem Index to determine if patients are candidates for the study. We will also require that they have a physical exam performed in the past 2 years. As documented by others, a domain score of >6 will indicate applicability for enrollment in either symptom or problem domain^{xi}. Additional inclusion criterion include: evidence of an absent UTI (e.g. negative urine

PROTOCOL TITLE: MYPAICE: Mindfulness and Yoga for Pain with Interstitial Cystitis Evaluation

dipstick, a negative urinalysis or urine culture) within 2 months of enrollment as well as ability to speak and understand English or Spanish. We will recruit only patients who will be undergoing first-line and second-line treatment, as defined by AUA and who have not made treatment changes to their regimen in the past 4 weeks.

Patients will be excluded if they have:

- unevaluated hematuria,
- a history of recurrent urinary tract infection (UTI), as defined by AUA criteria as >2 culture-proven UTIs in 6 months or 3 UTIs in one year within the last 5 years,
- urinary retention, defined as a post-void residual (PVR) of >150 mL confirmed by bladder scan or catheterization,
- a history of augmentation cystoplasty or urinary diversion,
- a history of cyclosporine A use
- a history of pelvic radiation or chemotherapy in the past 2 years
- history of radiation induced cystitis
- if patients are currently pregnant or lactating or planning on becoming pregnant in the next 3-4 months

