approximately 10 minutes of meditation daily via a commercially available app (either Calm App or Headspace App, both of which are commercially readily available) and approximately 15 minutes of yoga via the online tutorial. Yoga & use of the meditation app is estimated to take approximately 30 minutes per day. Patients may engage in any other of the 1st Line AUA therapies as well taking over the counter medications (Table 1). Patients will be called weekly to ascertain treatment compliance and monitor their progress. If symptoms are not improving there will be the option to discuss other treatment options (e.g. accelerate to higher lines of therapy based on AUA guidelines) at 6 weeks.

Women assigned to the Standard of Care alone group will receive any 1st Line and 2nd Line treatments (excluding use of the online yoga and meditation app). Patients will also be called weekly to monitor progress and to ensure no treatment effect secondary to phone calls. If symptoms are not improving there will be the option to discuss other treatment options (e.g. accelerate to higher lines of therapy based on AUA guidelines) at 6 weeks. At the termination of the study women in the standard of care group will receive 3 months of Calm App.

At the 6 week follow-up phone call patients will be given the option for escalation of therapy. Patients will be given the opportunity to escalate their treatment for IC/PBS to higher lines of treatments: use of intravesical Botox or use of sacral neuromodulation. We will record any accelerated therapy used by the patient that may be added during study participation.

For participants who have completed the study but treatment escalation data was not properly captured in RedCap surveys, These participants will be notified via email through RedCap to complete this additional survey.

Outcome measures:

GRA: The Global Response Assessment is a validated tool to assess response to treatment. It is comprised of a single question and has been utilized widely in IC/BPS^{xiii}. This will be collected weekly. However, the primary outcome is the 12 week (3 month) result.

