The patients enrolled are already opting for first line treatment of their IC/PBS and potential use of over the counter medications. Participation in this study may help to improve an individual participant's condition, but it is also possible that the condition may not improve. There is no guarantee that any individual will personally benefit by participating in this research study. Women assigned to the yoga and meditation group will also receive 1) a video that will instruct them on use of yoga that may help with IC/BPS symptoms (designed by a physical therapist who specializes in caring for IC/BPS patients) and 2) a meditation app. that will be provided to the patient for approximately 3 months (the study will pay for it for that length of time). Participation in this study may provide information that may help other people who have a similar medical problem in the future. The literature supports improvement of QOL in similar conditions such as endometriosis or primary dysmenorrhea.

19. Recruitment Methods

The Urogynecology clinics at UNM Eubank, and SRMC have a large referral population of patients with pelvic floor conditions such as IC/BPS. Subjects will be identified in the clinics at UNM Eubank clinic and SRMC by investigators

PROTOCOL TITLE: MYPAICE: Mindfulness and Yoga for Pain with Interstitial Cystitis Evaluation

when they present either in person or virtually (telephone or Zoom visits) for visits for IC/BPS care. The patients will be counseled about possible treatment options for IC/BPS and they will be introduced to the study and provided with written information that may help them decide if participation in the study is right for them. Subjects are encouraged to consult with family, friends, and primary health care providers, as well as communicate any questions they may have before beginning the written consent process. We will request a waiver of HIPAA authorization for recruitment purposes.

If a woman declines to participate or is withdrawn from the study either by her desire or that of the research staff, she will be offered the same treatment options. Her follow up appointments will be the same regardless of participation in the study.

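### The escalation endpoint counts 2nd-line therapy as escalation, although women may enter on it and the escalation record starts above it

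*Combined protocol and SAP*

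**What the plan says.** **Where women start.** Section 4.1 limits entry to women having first- and second-line treatment "who have not made treatment changes to their regimen in the past 4 weeks". Section 1.3(ii) states "Participants will start with 1st and 2nd Line therapy as recommended by the AUA guidelines" and makes the outcome the number who move to higher lines.

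**What the endpoint counts.** Section 7.1 lists as a secondary endpoint the proportion in each group on accelerated lines, and gives the range in brackets as 2 to 6.

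**What is recorded.** The therapy-escalation paragraph of section 12 says "We will record when and what women use that is greater than 1st line and 2nd line therapies", and adds that this record feeds the cost-utility analysis. Earlier in section 12, a more general sentence promises to record accelerated therapy added during participation. It follows directly on the naming of intravesical Botox and sacral neuromodulation as the higher lines.

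**Background care by arm.** Section 1.1 describes women "randomized to treatment with mindfulness and yoga + standard of care compared to standard care alone", and section 3 says "women will be randomized to either yoga & meditation + Standard of care compared to Standard of care alone". In section 12 the control sentence reads "Women assigned to the Standard of Care alone group will receive any 1st Line and 2nd Line treatments", with the study yoga and app excluded. The yoga-arm sentence reads "Patients may engage in any other of the 1st Line AUA therapies as well taking over the counter medications" and does not mention 2nd line.

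**The concern.** Three places define escalation, and they do not agree on whether 2nd line belongs to it. Table 1 puts manual physical therapy, several oral agents and bladder instillations in 2nd line, so this is a group of active treatments and not a marginal category. If they count, therapy that a woman brought with her can be scored as a failure of conservative care. If they do not, section 7.1 is wrong as written. Either way, two analysts could report different proportions from the same trial.

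The same record is the stated source for the cost-utility analysis. If that analysis is funded, 2nd-line costs would be missing from it.

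The background-care wording matters for a different reason. The stated target is yoga and mindfulness added to the same standard of care. A coordinator working from section 12 alone could take 2nd-line therapy to be open to controls and not to the yoga arm. The Global Response Assessment (GRA) is a single question on response to treatment, so it could not separate the two influences.

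**Working it through.** **1. The definitions side by side**

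| Place | Is 2nd line escalation? |
|---|---|
| Section 1.3(ii) | No: it is a starting line |
| Section 4.1 | No: it is permitted at entry |
| Section 7.1 | Yes: lines 2 to 6 |
| Section 12, therapy escalation | No: only therapy above 2nd line is recorded |
| Section 12, 6-week option | Names only Botox and neuromodulation, both 4th line in Table 1 |

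Section 7.1 stands alone.

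**2. What the literal endpoint measures.** The documents give no share of women on 2nd-line therapy at entry, so let it be s, equal in expectation across arms because of randomisation, and suppose that the therapy continues. Among the other women, let q(C) and q(Y) be the proportions in the control and yoga arms who start any of lines 2 to 6. The literal endpoint in an arm is s + (1 − s) × q, so the difference between arms is

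[s + (1 − s) q(C)] − [s + (1 − s) q(Y)] = (1 − s) × [q(C) − q(Y)].

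- s = 0: the endpoint is the proportion newly starting any of lines 2 to 6.
- s between 0 and 1: the difference shrinks by the factor (1 − s), and a move to lines 3 to 6 by a woman who entered on 2nd line adds nothing, because she is already counted.
- s = 1: both arms score 100% and the difference is zero whatever happens later.

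The therapy-escalation record yields the proportion using lines 3 to 6. It gives neither s nor the 2nd-line part of q, so the literal endpoint cannot be built from that record alone.

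**3. The background-care wording: illustration only.** The plan's own figure comes first. For 26% v 56% (mean 41%), two-sided 0.05 and 80% power,

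n = [1.960 √(2 × 0.41 × 0.59) + 0.842 √(0.26 × 0.74 + 0.56 × 0.44)]² / 0.30² = 40.99, or 41 per arm, as stated in section 5.3.

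Exact power of the uncorrected chi-square test at 41 per arm is 81.6%.

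Now suppose that section 12 were applied literally. Assume that a share of controls starts 2nd-line therapy, that each start raises the chance of response by a fixed number of points, that the planned 26% already includes this gain, and that the yoga arm loses it. The yoga rate is then 56% − share × gain.

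| Share starting | Gain (points) | Yoga v control | Exact power |
|---|---|---|---|
| 10% | 10 | 55.0% v 26% | 78.9% |
| 10% | 28 | 53.2% v 26% | 73.7% |
| 20% | 10 | 54.0% v 26% | 76.1% |
| 20% | 28 | 50.4% v 26% | 64.3% |

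The shares and gains are assumptions with no source in the documents. A 28-point gain nearly equals the whole 30-point target and is an upper case. The responder proportion stands in for the GRA mixed model.

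**The case against.** **The general recording sentence may already cover 2nd line.** Section 12 promises to record accelerated therapy added during the study, and section 7.1 uses the same word for lines 2 to 6. Section 12 also refers to REDCap surveys of escalation, with a further survey where capture failed, and baseline data include previous treatments for the condition. The survey items are not in the documents. This much stands: a reader might infer that the endpoint cannot be computed at all, and the documents do not support that. They do not settle the matter either, because the sentence's context is Botox and neuromodulation, and the paragraph that defines the outcome is narrower.

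**The arms are not clearly unequal.** The yoga-arm sentence permits and does not prohibit. Where section 12 restricts, as for controls, it says so. The yoga arm is headed as including standard of care, and the 6-week option skips 2nd line for everyone, which fits 2nd line already being open to both arms. This stands: a reader might infer that 2nd-line therapy is barred in the yoga arm, and the text does not say that.

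**The entry rule is ordinary.** A reader might see a fault in the four-week stability rule ending at entry. Eligibility criteria look back from entry, and free background care afterwards is a legitimate design. Differences in later treatment can be a consequence of assignment, and section 2 expects fewer interventions with yoga.

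**Section 18 is not a treatment rule.** Its remark that "The patients enrolled are already opting for first line treatment of their IC/PBS and potential use of over the counter medications" belongs to a description of benefits, and silence on 2nd line there excludes nothing.

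**Conclusion.** The point holds as an inconsistency in a secondary endpoint. Section 7.1 counts 2nd line; sections 1.3(ii) and 4.1 make it a permitted starting therapy, and the therapy-escalation record in section 12 leaves it out. This needs no numerical assumption. How far the literal endpoint would be diluted depends on the share of women on 2nd-line therapy at entry, which the documents do not give; the possible range runs from no dilution to no contrast at all.

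The missing mention of 2nd line in the yoga arm is a lesser matter, probably of drafting. Its effect on the primary outcome is unknown in size and direction. The power figures above describe one literal reading under assumed inputs and are not an estimate. Nothing here shows that the randomised comparison of the GRA is biased: it remains valid for the strategies as assigned.

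**What to change.** 1. **Section 7.1:** change the endpoint to lines 3 to 6, which matches sections 1.3(ii) and 12. This is the simpler choice and costs a wording change.
2. **Alternative, if 2nd line is meant to count:** count only 2nd-line therapies newly started after randomisation, and extend the section 12 record to 2nd-line starts, with dates, in both arms. The weekly calls already planned can carry this. The cost is one extra item per call. This option would also give the cost analysis its 2nd-line starts.
3. **Section 12, interventions:** state that both arms may use the same 1st- and 2nd-line therapies, apart from the study yoga video and meditation app in controls. The cost is one sentence.
4. **Analysis:** keep the primary comparison as randomised, and do not adjust for treatments started after allocation.
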